## 10.3.2 Efficacy

All scales included in Section 10.3.2 that are described as "clinician rated" are to be completed by the principal investigator or a delegated subinvestigator who is a licensed clinician. A licensed clinician is defined as a doctor of medicine, doctor of osteopathic medicine, or licensed psychologist with a PhD or another individual that is approved by the sponsor or designee. All raters are to be approved by the sponsor or designee.

## 10.3.2.1 Attention Deficit Hyperactivity Disorder Rating Scale Version 5

The ADHD-RS-5 (7) will be used as the primary measure. This parent-reported clinician-rated scale will be administered at each visit, beginning at Screening to capture the ADHD symptoms within each study week. The ADHD-RS-5 is a parent-reported/clinician-rated scale that was developed to measure the behaviors of children with ADHD, and comes in a Home Version and a School Version, with separate forms for children (ages 5-10 years) and adolescents (11-17 years); it consists of 18 items designed to reflect the symptomatology of ADHD based on the Diagnostic and Statistical Manual of Mental Disorders (DSM) DSM-5 criteria. Each item will be scored on a range of 0 (reflecting no symptoms) to 3 (reflecting severe symptoms) with total scores ranging from 0-54. The 18 items may be grouped into 2 subscales: inattention and hyperactivity/impulsivity. The Inattention subscale raw score is computed by summing the item scores for Items 1–9. The Hyperactivity–Impulsivity subscale raw score is computed by summing the item scores for Items 10–18. Additionally, the ADHD-RS-5 incorporates 2 impairment scales keyed to the inattention and hyperactivity–impulsivity dimensions, which allow the clinician to assess the extent to which ADHD-related problems adversely affect the home and/or school functioning of children and adolescents

Time of administration: 10-15 minutes

## 10.3.2.2 Clinical Global Impression-Improvement and Severity Scales

The CGI-I and CGI-S scales will be used as a secondary outcome measure for estimating level of functioning in response to NFC-1 treatment. These scales record the investigator's global assessment of the severity of the symptoms and changes in symptoms from Baseline based on reports from parents, subject, and minimal direct observation (8). This assessment will guide the investigator during dosing adjustments.

27 Oct 2016 AD-MW-07.04 29-Mar-2013 Version: Final Version v4.0 Page 33 of 58 A CGI-S scale captures the severity of a subject's condition on a 7-point scale ranging from 1 (normal, not at all ill) to 7 (among the most extremely ill subjects) (Table 2) on Baseline (Visit 2) and at Visit 8/ET.

At each visit from Visit 3 to Visit 8/ET, the investigator will assess the improvement of the subject's illness severity on the 7-point CGI-I scale ranging from 1 (very much improved) to 7 (very much worse) (Table 2).

The CGI-based assessments have been used to evaluate efficacy of ADHD medications (9), where they have general consistency and reliability.

*Time of administration: 10-20 minutes.* 

**Table 2:** Clinical Global Impression Scales

SEVERITY – CGI-S	
Normal, not at all ill	1
Borderline mentally ill	2
Mildly ill	3
Moderately ill	4
Markedly ill	5
Severely ill	6
Amongst the most extremely ill patients	7

IMPROVEMENT – CGI-I	
Very much improved	1
Much improved	2
Minimally improved	3
No change	4
Minimally worse	5
Much worse	6
Very much worse	7

Abbreviations: CGI-I = Clinical Global Impression of Improvement, CGI-S = Clinical Global Impression of Severity

## 10.3.2.3 Adolescent Sleep Hygiene Scale

The ASHS is a self-report questionnaire assessing sleep practices theoretically important for optimal sleep in adolescents aged  $\geq$  12 years of age. It assesses physiological (eg, evening caffeine consumption), cognitive (eg, thinking about things that need to be done at bedtime), emotional (eg, going to bed feeling upset), sleep environment (eg, falling asleep with the lights on), sleep stability (eg, different bedtime/wake time pattern on weekdays and at weekends), substance use (eg, evening alcohol use), daytime sleep (eg, napping), and having a bedtime routine.

The ASHS will be assessed at Baseline (Visit 2) and Visit 8/ET.

*Time of administration: 10 minutes.* 

## 10.3.2.4 Screen for Childhood Anxiety-related Emotional Disorders

The SCARED is a child self-report instrument for ages 8-18 years used to screen for childhood anxiety disorders including general anxiety disorder, separation anxiety disorder, panic disorder, and social phobia. In addition, it assesses symptoms related to school phobias.

The SCARED consists of 41 items and 5 factors that parallel the DSM-IV classification of anxiety disorders. The scale has good internal consistency, test-retest reliability, and discriminant validity, and it is sensitive to treatment response.

The SCARED will be assessed at Baseline (Visit 2) and Visit 8/ET.

*Time of administration: 10 minutes.* 

Version: Final Version v4.0

Page 34 of 58

## **10.3.3** Safety

Safety and tolerability assessments will include the frequency and severity of AEs as well as the evaluation of changes in clinical laboratory values, vital signs, ECG recordings, and C-SSRS.

## 10.3.3.1 Clinical Laboratory Safety Assessments

## 10.3.3.1.1 Clinical Laboratory Tests to be Performed

Samples for the following clinical laboratory tests will be collected at the time points specified in the schedule of events (Section 17.1).

Hematology Hemoglobin, hematocrit, red blood cell count, red blood cell indices,

mean corpuscular hemoglobin, mean corpuscular hemoglobin concentration, platelet count (or estimate), white blood cell count

including differential.

Serum chemistry Albumin, total bilirubin, total protein, calcium, alkaline phosphatase,

alanine aminotransferase, aspartate aminotransferase, blood urea nitrogen, creatinine, creatine kinase, glucose, sodium, potassium,

chloride, bicarbonate, lactate dehydrogenase, uric acid.

Urinalysis pH, specific gravity, blood, glucose, protein, ketones.

[Urine/serum] For women of childbearing potential only.

pregnancy test

Urine drug screen Amphetamines, barbiturates, benzodiazepines, cocaine, opiates,

phencyclidine, cannabinoids, propoxyphene and methadone.

Blood samples will be collected as specified in the study laboratory manual.

Laboratory specimens will be analyzed at the central laboratory as specified in the study laboratory manual.

## 10.3.3.1.2 Biological Markers

Not applicable.

## 10.3.3.1.3 Specimen Handling Requirements

The transmission of infectious agents may occur through contact with contaminated needles and blood or blood products. Consequently, appropriate blood and body fluid precautions should be employed by all study personnel involved in the collection of blood and handling of specimens in both the clinic and laboratory settings. Refer to current recommendations of the appropriate authorities.

In addition to appropriate handling of subject samples, specific regulations exist regarding the shipment of biologic/etiologic samples. Procedures and regulations for the packaging and shipping of infectious samples are outlined in the study laboratory manual. The investigator is responsible for ensuring that all study samples that are to be transported to another location are appropriately packed and shipped according to the applicable regulations.

## 10.3.3.1.4 Evaluation of Laboratory Values

The normal ranges of values for the laboratory assessments in this study will be provided by the responsible laboratory and submitted to Medgenics, Inc. prior to the beginning of the study. They will be regarded as the reference ranges on which decisions will be made.

If a laboratory value is out of the reference range, it is not necessarily clinically relevant. The investigator must evaluate the out-of-range values and record his/her assessment of the clinical relevance in the appropriate eCRF.

All laboratory values which, in the investigator's opinion, show clinically relevant or pathological changes during or after termination of the treatment are to be discussed with the medical monitor and reported as AEs and followed, as described in Section 11.2.5.

All measurements described in this section are recognized standard methods.

#### **10.3.3.2 Clinical Examinations**

## **10.3.3.2.1 Vital Signs**

Vital signs, including heart rate, respiratory rate, and systolic and diastolic blood pressure will be measured after the subject has been in a sitting position for 5 minutes.

## 10.3.3.2.2 Electrocardiogram

A standard 12-lead ECG will be performed after the subject has been supine for at least 5 minutes. All ECG recordings will be identified with the subject number, subject initials, date, and time of the recording and will be attached to the subject's eCRF.

All ECG values which, in the investigator's opinion, show clinically relevant or pathological changes during or after termination of the treatment are to be discussed with the medical monitor and reported as AEs and followed, as described in Section 11.2.5.

## 10.3.3.2.3 Physical Examination

A complete physical examination (excluding the genitourinary examination) will be performed at Visit 1 before potential exposure to the IP and at Visit 8 at the completion of exposure.

## 10.3.3.3 Columbia Suicide Severity Rating Scale

The C-SSRS (10) is a semi-structured interview that captures the occurrence, severity, and frequency of suicide-related thoughts and behaviors during the assessment period. The interview includes definitions and suggested questions to solicit the type of information needed to determine if a suicide-related thought or behavior has occurred. The interview and rating for the C-SSRS must be completed by a licensed clinician and is medically responsible for the subject. A licensed clinician is defined as a doctor of medicine, doctor of osteopathic medicine, or licensed psychologist with a PhD. The C-SSRS has a "baseline" version which will be completed at Screening (Visit 1) and a "Since Last Visit" version that will be completed at all subsequent visits. There are a maximum of 19 items to be completed: 7 that are required, 10 potential additional items if there is a positive response to a required item, and 2 items for suicide/suicide behavior present during the interview. The C-SSRS uses dichotomous scales (ie, yes or no), Likert scales, and text or narrative to further describe the thoughts or behaviors.

*Time of administration* = 10 *minutes.* 

#### 10.3.3.4 Adverse Events

The definitions and management of and special considerations for AEs are provided in Section 11.

### 11. ADVERSE EVENTS

#### 11.1 Definitions

#### 11.1.1 Adverse Events

An AE is defined as any untoward medical occurrence in a patient or clinical investigation subject administered a pharmaceutical product that does not necessarily have a causal relationship with the product. An AE can therefore be any unfavorable and unintended sign (including a new, clinically important abnormal laboratory finding), symptom, or disease, temporally associated with the product, whether or not related to the product.

Pre-existing diseases or conditions will not be considered AEs unless there is an increase in the frequency or severity, or a change in the quality, of the disease or condition (worsening of a pre-existing condition is considered an AE).

Events occurring in subjects treated with placebo or during treatment-free periods of the study are also considered AEs.

# 11.1.2 Unexpected Adverse Event

An expected AE is one for which the nature or severity is consistent with the known AE profile of the product. For an IP, the known information is contained in the IB. For a marketed product, the known information is contained in the current package insert for the product.

An unexpected AE is one for which the specificity or severity is not consistent with the current IB. For example, hepatic necrosis would be unexpected (greater severity) if the IB only listed elevated hepatic enzymes or hepatitis. Likewise, cerebral thromboembolism and cerebral vasculitis would be unexpected (greater specificity) if the IB only listed cerebral vascular accidents.

Furthermore, reports that add significant information on specificity or severity of a known, already documented adverse reaction constitute unexpected events. Examples would be (a) acute renal failure as an expected adverse reaction with a subsequent new occurrence of interstitial nephritis (interstitial nephritis would be unexpected) and (b) hepatitis with a first occurrence of fulminant hepatitis (fulminant hepatitis would be unexpected).

## 11.1.3 Serious Adverse Events

An SAE is any untoward medical occurrence that at any dose:

- Results in death.
- Is life-threatening.

NOTE: The term "life-threatening" in the definition of "serious" refers to an event in which the subject was at risk of death at the time of the event; it does not refer to an event which hypothetically might have caused death if it were more severe.

- Requires inpatient hospitalization or prolongation of existing hospitalization.

  NOTE: Inpatient hospitalization is defined as 24 hours in a hospital or an overnight stay. An elective hospital admission to treat a condition present before exposure to the test drug, or a hospital admission for a diagnostic evaluation of an AE, does not qualify the condition or event as an SAE. Further, an overnight stay in the hospital that is only due to transportation, organization, or accommodation problems and without medical background does not need to be considered an SAE.
- Results in persistent or significant disability/incapacity.

• Is a congenital anomaly.

NOTE: A congenital anomaly in an infant born to a mother who was exposed to the IP during pregnancy is an SAE. However, a newly diagnosed pregnancy in a subject that has received an IP is not considered an SAE unless it is suspected that the IP(s) interacted with a contraceptive method and led to the pregnancy.

• Is an important medical event.

NOTE: Medical and scientific judgment should be exercised in deciding whether it is appropriate to consider other situations serious, such as important medical events that may not be immediately life-threatening or result in death or hospitalization but may jeopardize the subject or may require intervention to prevent one of the other outcomes listed in the definition above. Examples of such events are intensive treatment in an emergency room or at home for allergic bronchospasm, blood dyscrasias or convulsions that do not result in hospitalization, or development of drug dependency or drug abuse.

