### 11.2.6.2 Non-serious Adverse Events

Nonserious AEs will be recorded in the eCRF and reported by

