## 11.3 Special Considerations

# 11.3.1 Adverse Events of Special Interest

The following events will be considered as AEs of special interest during this study:

- Psychosis.
- Suicidal ideation.

Based on the population under study, and their age, suicidal ideation will be considered as an AE of special interest.

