### 12. DATA SAFETY MONITORING BOARD

No Data Safety Monitoring Board will be required.

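### Protocol 11.1.3 exempts admissions for diagnostic evaluation of an AE from the SAE definition, so an admission to assess suicidal ideation or psychosis can lose the SAE label and 24-hour reporting

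*Protocol*

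**What the plan says.** Protocol Section 11.1.3 lists as a seriousness criterion an event that "Requires inpatient hospitalization or prolongation of existing hospitalization". The NOTE beneath it adds: "Inpatient hospitalization is defined as 24 hours in a hospital or an overnight stay". That definition depends on length of stay, not on purpose.

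The NOTE then sets out three exclusions:

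- elective admission to treat a condition that was there before exposure;
- admission for diagnostic work-up: "or a hospital admission for a diagnostic evaluation of an AE, does not qualify the condition or event as an SAE";
- an overnight stay due only to transport, organization or accommodation.

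The important-medical-event criterion follows in the same section: "Medical and scientific judgment should be exercised in deciding whether it is appropriate to consider other situations serious". Section 11.2.2.2 has the investigator decide seriousness by reference to 11.1.3. Section 11.2.6.1 sets a 24-hour reporting duty for SAEs.

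Section 11.3.1 states: "The following events will be considered as AEs of special interest during this study". It lists psychosis and suicidal ideation, and gives a reason for the second: "Based on the population under study, and their age, suicidal ideation will be considered as an AE of special interest". It attaches no form, recipient or timeline to either.

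**The concern.** The first and third exclusions cover admissions that say little about drug safety. The second is different. It applies to an AE, which may be new and on treatment, and which was worrying enough for the adolescent to be admitted. It has no limit on urgency or length of stay and no exception for the two events the protocol singles out.

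Two things are at stake. One is timing: the sponsor may not hear of such an admission within 24 hours. The other is consistency of the SAE count. The Protocol plans about 35 sites with roughly 2 to 3 randomized subjects each (Section 7.3), and the SAP about 25 sites (Section 3). The same kind of admission could be classed differently by different investigators, each following the text. That count feeds SAP Table 14.3.1.5 and the SAE row of Table 14.3.1.1.

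**Working it through.** The point concerns the wording of a definition, and the plan gives no figure to reproduce. The check is to follow one event through the sections.

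1. **Event.** A subject on treatment develops suicidal ideation or psychotic symptoms and is kept overnight, unplanned, only for evaluation.
2. **Length of stay (11.1.3).** An overnight stay meets the definition of inpatient hospitalization, so up to here the event is serious.
3. **Exclusion (same NOTE).** The admission was for diagnostic evaluation of an AE, so it does not make the event an SAE. The exclusions for elective and for logistical stays are not needed to reach this result and do not limit it.
4. **Remaining criteria (11.1.3).** Death, disability and congenital anomaly do not apply to this example. Life-threatening applies only if the subject was at risk of death at the time of the event. Important medical event is open to the investigator's judgment.
5. **Reporting.** If the investigator applies one of those two criteria, the 24-hour duty in 11.2.6.1 applies. If not, the event is non-serious and that duty does not apply.
6. **Special-interest route (11.3.1).** None is stated, so step 5 is not overridden.

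Two features of 11.1.3 make steps 3 and 4 hard to apply uniformly:

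- **Mixed admissions.** The exclusion covers admission for diagnostic evaluation. Admission for protection or treatment falls outside it and meets the hospitalization criterion. The section does not say how to class a stay that serves both purposes, and a psychiatric stay may well do so.
- **The convulsion example.** The important-medical-event examples include convulsions that did not lead to hospital admission. A convulsion followed by an overnight diagnostic stay does not qualify through hospitalization and also falls outside that example's wording. An investigator could still call it serious, but would be going beyond the example to do so.

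Elsewhere the protocol does write special routes. Section 11.3.2 gives pregnancy its own 24-hour report. Sections 10.3.3.1.4 and 10.3.3.2.2 send clinically relevant laboratory and ECG changes to the medical monitor. The C-SSRS section (10.3.3.3) and Section 11.3.1 contain no comparable instruction.

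What the analysis would still show:

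| Output | Non-serious event still shown? |
|---|---|
| TEAE incidence, relationship and severity (SAP Tables 14.3.1.2, 14.3.1.8, 14.3.1.9) | Yes |
| C-SSRS (SAP Table 14.3.6) | Yes, for suicidal ideation |
| SAE incidence (SAP Table 14.3.1.5) | No |
| Separate summary of AEs of special interest | None planned in SAP Section 9 |

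**The case against.** The strongest reply is that the exclusion removes one criterion only. The protocol says judgment should be used on important medical events. That criterion is written for events that endanger the subject or need intervention to prevent a listed outcome, and death is a listed outcome. Suicidal ideation serious enough to prompt admission fits that description well. The examples are illustrative, they include drug dependency and abuse, and they exclude neither special-interest event. All of this stands, and it makes the loss possible rather than automatic. It does not remove the problem, because the result then depends on each investigator's judgment instead of the plain hospitalization rule.

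It is also fair to say that many psychiatric admissions are protective or therapeutic and so remain serious through hospitalization. That stands for clear cases. Mixed cases are left unresolved.

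A reader might infer more than the text supports:

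- **That these admissions never reach 24-hour reporting.** They do whenever another criterion is applied.
- **That the events disappear from the report.** The C-SSRS is done at every clinic visit, and TEAEs are tabulated whether serious or not.
- **That Section 11.2.6.2 proves there is no prompt route for non-serious events.** The end of its sentence is blacked out, so nothing can be concluded from it.
- **That the absence of a data safety monitoring board is part of the fault.** Such a board reviews accumulating data and would not settle how one admission is classed or how fast it is reported.

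**Conclusion.** The point holds as a possible loss of the SAE label and its timing. Read as written, 11.1.3 allows an unplanned overnight admission to evaluate a new AE, including psychosis or suicidal ideation, to be recorded as non-serious. Neither 11.3.1 nor 11.2.6.1 corrects that. The effect is limited to SAE classification, the SAE tables and the speed of notice to the sponsor.

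No numerical size can be given, because the documents state no rate of hospital admission and no expected frequency of either special-interest event. The conclusion assumes that the admission is purely diagnostic, or is read that way, and that the investigator does not apply the life-threatening or important-medical-event criterion. That sites would in fact diverge is a reasonable expectation from the wording, not something the documents show. Because the change is cheap and concerns the timeliness of safety reporting in adolescents, it should be made.

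**What to change.** 1. **Section 11.1.3.** Delete from the NOTE the alternative covering admission for diagnostic evaluation of an AE. Keep the exclusion for elective admissions for pre-existing conditions and the one for transport, organization or accommodation stays. A 24-hour or overnight stay for a new AE then counts whatever its purpose, and the mixed-admission question no longer arises.
2. **Section 11.3.1, reconciled with 11.2.6.1.** State that an AE of special interest leading to hospital admission is reported on the SAE form within 24 hours.

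The second change alone would restore timely notice for the two named events. The first is needed for a consistent SAE count and for other new AEs. The added sentence is limited to events that lead to admission. Expedited reporting of every special-interest event would be a wider policy, which this point does not require.

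The cost is one deleted clause and one added sentence in an amendment, a few more expedited forms, and some observation-only admissions counted as SAEs. Treatment, dosing and the efficacy analysis are not affected.
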